12. SAMPLE GROUP AND TOTAL NUMBER OF PARTICIPANTS

The subjects to be considered will be all those interested in participating who respond to the national advertising campaign that will be launched. They will be contacted by e-mail or telephone, and the questionnaires and selection records will be sent by e-mail (the criteria for inclusion in the study are defined in the following section).

All patients who come to the MSI requesting evaluation and treatment for PE and who meet the inclusion criteria will also be able to participate in the study. Subjects will be free to leave the study at any time and will not receive financial compensation for participating, although they will receive a gift at the end of the study, and a high drop-out rate is expected.

Based on randomized studies to assess the efficacy of treatments for premature ejaculation in which there was a control group, we estimate that 24 subjects per group will be needed to establish the differences between the two groups, considering a statistical power of 0.80 and alpha of $p=0.05$.

13. PATIENT INCLUSION AND EXCLUSION CRITERION

Inclusion criteria for selection will be: aged 18 or over, in a heterosexual relationship for at least the last 6 months, having a score greater than 11 on the PEDT (Premature Ejaculation Diagnostic Tool) and a mean self-reported IELT (Intravaginal Ejaculatory Latency Time) of <120 seconds.

Exclusion criteria will include: History of alcohol abuse or dependence, having received medication or psychological treatment for PE in the last 3 months, having diabetes, or a regular use of recreational drugs (except tobacco and caffeine).

14. STATISTICAL ANALYSIS

As the main evaluation parameter, the "fold change" of the IELT will be used, which will be calculated using the geometric averages of the post-treatment IELT (period B) divided by the average of the IELT at the beginning of the treatment that served as a baseline (period A).

The Mahalanobis distance test will be used to check the existence of outliers (with a Z score of > 3) and the Kolmogorov-Smirnov test to check the goodness of fit of the data and the Square Root Transformation in those cases where the assumption of normality is not met.

The Greenhouse-Geisser method will be used to correct for degrees of freedom when the sphericity assumption is not met.

The MANOVA contrast will be performed for the demographic variables, and, presumably, we will find significant differences in variables such as age.

For the contrasts, ANCOVAs of independent measurements will be used, with the variables that have come out as significant in the MANOVA contrast as covariates, to check the differences between the two experimental groups and the equality between baselines in each of the study variables. And, similarly, ANCOVAs of repeated measurements to check the existence of the benefits of each therapy on the baseline.

All p values should be bilateral and the significance level used < 0.05. The IBM SPSS Statistics version 22 statistical package should be used.

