9. DESIGN AND RATIONALE

In both groups, and to enable both groups of subjects to access treatment for PE, the control will be intra-subject. The main variables and data to establish the baseline of each group will be collected during a period of a similar length to the treatment period.

-This research project will use two experimental groups. One will be given the "sct" therapy (experimental group 1) and the other will be given the "start-stop" therapy combined with the external device (experimental group 2). The two groups will receive parallel therapy with the same exercise protocol (with the only difference being that, in experimental group 2, the sct exercises will be carried out with the device in question). The participants who meet the selection criteria will be randomly assigned to an experimental group, along with its corresponding conditions.

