10. MAIN OBJECTIVE

The aim of the project is to demonstrate the effectiveness on PE of the "sct" combination treatment adapted from Semans (1956) within the framework of an exercise program carried out with an new external device specific design for this method .

Its effectiveness on PE will be reflected in increased intravaginal ejaculation latency times (IELT) and subjective perception scores from baseline therapy. The increased efficacy of the combination therapy ("sct" in conjunction with external device) will be reflected in the greater increase in IELT and subjective perception scores from combination therapy over "sct" therapy. The level of scientific evidence will indicate the competitiveness and efficacy of this cognitive-behavioral psychological technique.

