16. DURATION OF THE TREATMENT

The duration of the treatment will be 7 weeks, during which the previously-explained exercises will be carried out.

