Waldinger, M. D., Zwinderman, A. H., Olivier, B., & Schweitzer, D. H. (2008). Geometric Mean IELT and Premature Ejaculation: Appropriate Statistics to Avoid Overestimation of Treatment Efficacy. *The Journal of Sexual Medicine*, 5(2), 492–499

Collaborator's signature:
Instituto Sexológico Murciano

INSTITUTO SEXOLOGICO MURCIANO
N.R.S 20300055
[contact]
www.isemu.es | [contact]

Lead Researcher's signature
[name]

Annexed 1

Data collection forms

REGISTER OF EJACULATION TIMES

[figure not shown]
[figure not shown]
[figure not shown]
[figure not shown]
[figure not shown]
[figure not shown]
[figure not shown]
[figure not shown]
[figure not shown]
[figure not shown]
[figure not shown]
[figure not shown]

[figure not shown]
WEEK:

NAME:

MONDAY TUESDAY WEDNESDAY THURSDAY FRIDAY SATURDAY SUNDAY

[figure not shown]
[figure not shown]

[figure not shown]

[figure not shown]
[figure not shown]
[figure not shown]
[figure not shown]
[figure not shown]
[figure not shown]

MASTURBATION

Record the time you take to ejaculate when masturbating

[figure not shown]
PENETRATION INTERCOURSE

Record the time you take to ejaculate after penetration

Annexed 2

ANEXO 2

[figure not shown]

PARTES.

1 – Pines magnéticos de carga

2 – Rosca hembra para aplique de manos libres.

- 3 – Rosca reguladora de succión.
- 4 - Botonera para control de vibración y calefacción.
- 5 – Conexión con resistencia calefactora
- 6 – Orificio de entrada de la manga
- 7 – Motor vibrador
- 8 – Bolsillo para albergar el motor vibrador.
- 9 – Palo calefactor.
- 10 y 11 – Sistema de imanes para asegurar el cierre.

**DIMENSIONES
PRINCIPALES**

MATERIALES Y PESO

PARTE	MATERIAL
MANGA	TPE (Elastómero termoplástico)
CUERPO	ABS
PALO CALEFACTOR	
RECUBRIMIENTO DEL CUERPO "SOFT TOUCH"	PDMS ("Silicona soft touch")

[figure not shown]
PARTE	PESO (gramos)
MANGA	340
MYHIXEL I (con manga)	670

MYHIXEL I (en uso, sin calefactor)	560
------------------------------------	-----

ELECTRONICA Y FUNCIONES

PARTE	MATERIAL
BATERÍA	POLÍMERO DE LITIO (650 Ma 3.7 V)
MOTOR VIBRADOR	~2 V (3.5 mm y 100 HZ)
CALEFACCIÓN	RESISTENCIA EN POLIAMIDA
CARGA	PINS MAGNÉTICOS + USB

1	2	3	4	5	6
LED 1+2	LED 1+2	LED 1+2	LED 1	LED 1	LED 2
CARGANDO	CARGADO	BATERÍA BAJA	CALENTANDO	TEMPERATURA ALCANZADA	VIBRACIÓN
Leds ON fijo	Leds OFF	Los leds parpadean alternativamente	Led ON Latente (ver link adjunto)	Led OFF	Led On Durante 10 sg y luego OFF

COLOR LEDS (1 y 2): **BLANCO CÁLIDO**

APPENDIX 3

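### As written, the primary fold change divides a geometric mean by an ordinary mean, so its typical no-change value is below 1 and each arm's gain over baseline is understated

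*Protocol*

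**What the plan says.** Section 14 (Statistical Analysis) fixes the primary measure as a fold change in IELT, "calculated using the geometric averages of the post-treatment IELT (period B) divided by the average of the IELT at the beginning of the treatment"; the denominator is the baseline, period A. The qualifier geometric stands with period B only, and the words arithmetic or plain appear nowhere. The section does not say whether the averaging runs over one man's records or over the men in an arm.

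Four other places bear on the point:

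- Section 9 makes the control intra-subject and says that the baseline data "will be collected during a period of a similar length to the treatment period". Section 16 states: "The duration of the treatment will be 7 weeks".
- The form in Annex 1 has a column for each day and a row for times during intercourse, so a man can contribute several records in a period.
- Section 10 makes the change from baseline an aim in its own right: "Its effectiveness on PE will be reflected in increased intravaginal ejaculation latency times (IELT"). Section 14 adds repeated-measures ANCOVAs for the benefit of each therapy over baseline.
- Section 11 supports IELT with a paper listed in Section 20 as "Geometric Mean IELT and Premature Ejaculation: Appropriate Statistics to Avoid Overestimation of Treatment Efficacy".

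**The concern.** For positive times that vary, the arithmetic mean is larger than the geometric mean. A ratio with a geometric mean on top and an arithmetic mean below therefore does not centre on 1 when latency has not changed. The gap depends on how variable the baseline times are and how many were recorded. Neither has anything to do with treatment.

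The trial has no untreated arm. The evidence that either therapy works at all is the gain over each man's own baseline, and that is the quantity the mismatch distorts. An analyst who follows Section 14 to the letter and one who follows the cited method would report different values of the primary measure from the same data.

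**Working it through.** **No figure to reproduce.** The Protocol gives no expected fold change, no SD of IELT and no number of records per man. The check uses its formula with assumed inputs over a range.

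**Inputs from the Protocol.** Geometric mean in period B and an unqualified average in period A (Section 14); a baseline about as long as the 7-week treatment (Sections 9 and 16); daily entries on the form (Annex 1).

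**Assumptions.** IELT is log-normal within a man. The within-man SD of log IELT, s, is 0.3, 0.5 or 0.7. The number of records per period, k, is 1, 2, 4 or 14 (14 being two a week for 7 weeks). The true distribution is the same in both periods.

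**Step 1: one man with identical records in both periods.** Take 30, 45, 60 and 90 s.

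- Geometric mean: (30 × 45 × 60 × 90)^(1/4) = 7,290,000^(1/4) = 51.96 s
- Arithmetic mean: (30 + 45 + 60 + 90)/4 = 56.25 s
- Fold change as written: 51.96/56.25 = 0.924
- Fold change with geometric means in both periods: 51.96/51.96 = 1

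**Step 2: independent records in the two periods.** The ratio splits into two factors:

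GM(B)/AM(A) = [GM(B)/GM(A)] × [GM(A)/AM(A)]

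The first factor is the intended fold change. The second uses baseline data only. Its typical (geometric mean) value is about exp(-(s²/2)(1 - 1/k)). For s = 0.5 and k = 14 this is exp(-0.125 × 13/14) = exp(-0.116) = 0.890.

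Typical fold change of an unchanged man, approximation first and simulation (200,000 men per setting) second:

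| Records k | s = 0.3 | s = 0.5 | s = 0.7 |
|---|---|---|---|
| 1 | 1.00 / 1.00 | 1.00 / 1.00 | 1.00 / 1.00 |
| 2 | 0.978 / 0.978 | 0.939 / 0.943 | 0.885 / 0.894 |
| 4 | 0.967 / 0.968 | 0.911 / 0.913 | 0.832 / 0.841 |
| 14 | 0.959 / 0.959 | 0.890 / 0.891 | 0.797 / 0.799 |

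With geometric means in both periods, the simulated value is 1.00 in every cell.

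**Step 3: what this does to a real gain.** The factor multiplies the true fold change. At s = 0.5 and k = 14, a true 1.2-fold gain reads as about 1.2 × 0.89 = 1.07.

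**Step 4: individual men.** The shift is in the typical value. At s = 0.5, about 72% of unchanged men fall below 1 with 14 records and about 55% with 2, against 50% when the means match.

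**Step 5: the comparison between arms.** The second factor in Step 2 depends only on period A, so randomisation balances it in expectation. Simulating 24 men per arm with 14 records, no effect and a t-test on log fold change (6,000 replicates), the two-sided type I error for s = 0.3, 0.5, 0.7 was 0.049, 0.047, 0.050 with mixed means and 0.053, 0.048, 0.050 with matched means. The mean arm difference was about 0. The SD of that difference rose by about 1%, 3% and 6%.

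**The case against.** The strongest reply is that the text never says arithmetic. The plural in the Section 14 definition can be read to cover both periods, and the cited source is about geometric mean IELT. That is a fair account of what was probably intended, and it stands to that extent. It does not settle the formula: the qualifier is attached to one period only, the ordinary meaning of an unqualified average is the arithmetic mean, and no other section corrects it.

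The number of baseline records is also uncertain. Section 9 implies a long baseline, but Section 14 places it at the start of treatment, Section 19 describes registration after each week of treatment, and Section 18 fits inclusion and treatment into June to August 2019. The shift may therefore be nearer the 2-record row than the 14-record row. This is why a range is given.

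The direction is conservative: the mismatch lowers the apparent gain and does not favour a claim of benefit. That is correct, but a primary measure that understates its own effect is still wrong.

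A reader might infer three stronger things that the Protocol does not support:

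- **Every unchanged man scores below 1.** He need not (Step 4), and with one baseline record there is no shift.
- **An ineffective therapy would often be declared significantly harmful.** That would need a test of the fold change against 1. Section 14 names no such test; it plans ANCOVAs between groups and over repeated measurements.
- **The arm comparison is biased unless baseline variability and intercourse frequency happen to match.** Randomisation balances them in expectation, and the loss of precision is small when the ratio is formed per man. A ratio formed over a whole arm would bring in the spread between men and lose more, but it gives one number per arm and could not enter the planned ANCOVAs.

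**Conclusion.** The point holds as a defect in the written definition of the primary measure. Taken literally, Section 14 gives a fold change whose typical no-change value is below 1: about 0.98 to 0.89 with 2 baseline records, 0.97 to 0.84 with 4 and 0.96 to 0.80 with 14, for within-man log SD from 0.3 to 0.7. Each arm's gain over baseline is understated by the same factor. The size rests on log-normal IELT and on assumed SDs and record counts; the direction needs only baseline times that vary and more than one of them.

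The consequence is confined to the within-arm gain. That still matters here, because the control is intra-subject, no arm is untreated, and benefit over baseline is a stated aim. The between-arm conclusion is not put at risk beyond a few percent in the SD.

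**What to change.** In Section 14, insert the word geometric before average for period A, so that both periods use the same mean. State that the fold change is computed for each man as exp(mean log IELT in period B minus mean log IELT in period A). No change then equals 1, whatever a man's variability or number of records. Analysing that difference on the log scale follows naturally; the details can sit in the SAP.

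The cost is one sentence. The same IELT records are used, and no extra data or patients are needed.

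### Section 14 defines the primary IELT fold change as a geometric mean over an unqualified average and names no analysis scale that matches a ratio of geometric means

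*Protocol*

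**What the plan says.** Section 14 (Statistical analysis) makes the fold change in IELT the main evaluation parameter: "geometric averages of the post-treatment IELT (period B) divided by the average of the IELT at the beginning of the treatment". The period B mean is called geometric; the period A mean is not qualified.

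The same section applies "the Square Root Transformation in those cases where the assumption of normality is not met", with a Kolmogorov-Smirnov test as the check. It mentions no log transformation.

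On testing it says: "For the contrasts, ANCOVAs of independent measurements will be used", "to check the differences between the two experimental groups and the equality between baselines in each of the study variables". For change within an arm it plans "ANCOVAs of repeated measurements to check the existence of the benefits of each therapy on the baseline". It does not say whether the dependent variable for the primary comparison is the fold change or IELT in seconds, or whether the fold change is formed per man or per group.

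Section 10 (Main objective) makes two efficacy claims: a gain over baseline, and an added value of the device "reflected in the greater increase in IELT and subjective perception scores from combination therapy" over the exercise therapy alone.

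**The concern.** A fold change should equal 1 when nothing changes. A geometric mean over an arithmetic mean does not: whenever the baseline values vary, the arithmetic mean is the larger, so the expected no-effect value lies below 1 and depends on the baseline spread. Two analysts reading Section 14 could therefore report different primary results from the same data.

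The second weakness is the scale. A ratio of geometric means is a difference of mean logs. The plan offers raw seconds or, if a pre-test rejects normality, square-root seconds. Neither yields that ratio, and a small-sample test decides between them. At stake are the fold change reported for each arm, some power, and a clear link between the primary endpoint and its test.

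**Working it through.** **The plan's own figure.** The Protocol gives no expected fold change and no IELT spread. Its one computed design figure is 24 per group (Section 12; power 0.80, alpha 0.05). Solved backwards, this implies a standardized difference of (1.960 + 0.842) × √(2/24) = 0.81, or 0.83 with the t-distribution. That figure is not in dispute and says nothing about the scale, so every spread below is an assumption.

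**Inputs from the Protocol.** Mean baseline IELT under 120 s (Section 13). Baseline collected over a period about as long as treatment (Section 9). A recording form with a column for each day (Annexed 1). 50 men with 30% dropout (Section 5.11), so 50 × 0.70 = 35 men, or 18 and 17 per arm.

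**1. No-effect value, log-normal times.** Geometric mean / arithmetic mean = exp(−σ²/2), with σ² = ln(1 + CV²).

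| Assumed CV | No-effect value | True fold change needed to score 1 |
|---|---|---|
| 0.3 | 0.96 | 1.04 |
| 0.5 | exp(−0.223/2) = 0.89 | 1.12 |
| 1.0 | exp(−0.693/2) = 0.71 | 1.41 |

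**2. Group-level ratio, baselines cut at 120 s** (simulated):

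| Median before cut | log-SD 0.4 | log-SD 0.6 | log-SD 0.8 |
|---|---|---|---|
| 30 s | 0.92 | 0.85 | 0.78 |
| 45 s | 0.93 | 0.87 | 0.82 |
| 60 s | 0.94 | 0.90 | 0.85 |

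A true doubling would read between 2 × 0.784 = 1.57 and 2 × 0.938 = 1.88.

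**3. Per-man ratio.** Here only within-man spread matters. With 4 to 14 records per man, the no-effect value is 0.96-0.99 at a within-man log-SD of 0.2-0.3, and 0.89-0.91 at 0.5.

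**4. Sampling variation.** With 24 uncut log-normal values per period and log-SD 0.3, 0.5 and 0.8, the no-effect median is 0.96, 0.89 and 0.74, and the chance of a result below 1 is 0.69, 0.79 and 0.89. With geometric means in both periods the median is 1.00 and that chance is 0.50.

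**5. Between arms.** With equal baseline spread the factor cancels. Simulating 18 and 17 men with a true ratio of 1.8 (log-SD 0.4-0.8, correlation 0.5) gives a median between-arm ratio of 1.80 under both definitions. The mixed definition makes the SD of the log ratio 4-15% larger.

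**6. Square-root scale.** The same threefold gain is √120 − √40 = 4.63 from a 40 s baseline and √180 − √60 = 5.67 from 60 s, so equal fold changes look unequal.

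**7. The pre-test.** For log-normal data with log-SD 0.5-0.9, the uncorrected Kolmogorov-Smirnov test rejects in about 1-10% of samples at n = 17 and about 2-22% at n = 25. With the Lilliefors correction it rejects in 28-83% over these sizes. Section 14 does not say which version applies.

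**8. Power, one scenario** (18 and 17 men, between-arm ratio 1.8, log-SD 0.8, correlation 0.5, log-normal data). Separate simulations gave about 52-53% on raw seconds, 60-66% on the square root and 62-69% on the log. Within each run the square root was 2 to 4 points below the log.

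**The case against.** The best defence is that *average* is shorthand. The phrase begins with geometric averages, and Section 11 supports the IELT measure with a reference whose title concerns geometric mean IELT and avoiding overestimated efficacy. Geometric means in both periods may well be intended. This stands as a probable reading, but the text does not say it, and this is the definition of the primary endpoint.

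A second defence is that a single baseline value per man would remove the bias from a per-man ratio. Section 9 and the daily form point to several records per man, so it fits poorly.

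A reader might go further than the Protocol allows in four ways:

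- *The test does not address the endpoint.* Not established. The ANCOVAs cover each study variable, which may include the fold change; the fault is that the link is not stated.
- *The tests use square roots.* Only conditionally, and the uncorrected pre-test would seldom trigger them.
- *The treatment comparison is biased, or benefit could be falsely claimed.* The factor largely cancels between arms when baseline spread is equal, as randomisation gives in expectation. Within an arm it runs against the treatment.
- *A planned confidence interval is invalid.* Section 14 plans none.

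It is also fair that log-normal simulation favours the log by construction, and that the square root costs little power against it.

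**Conclusion.** The point holds in a limited form. Read literally, the primary fold change has a no-effect value below 1 in expectation, though not in every sample. The size rests on assumed spreads: 0.78-0.94 for a group-level ratio, 0.96-0.99 for a per-man ratio with small within-man spread, and a loss of only 2-4% at a CV of 0.2-0.3. The harm is to each arm's reported gain over baseline, which is one of the two efficacy claims in Section 10. The between-arm ratio loses some precision but is essentially unbiased when baseline spread is equal.

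Separately, the tested variable is not tied to the endpoint, and neither scale on offer estimates a ratio of geometric means. The main power loss would come from analysing raw seconds, the default when the pre-test does not reject; this rests on one log-normal scenario. Severity: should be fixed. Confidence: moderate, because the intended meaning of the baseline average is uncertain.

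**What to change.** In Section 14:

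1. State geometric means for both periods, and that the fold change is formed per man: log geometric mean IELT in period B minus log geometric mean IELT in period A.
2. Name that log fold change (or log IELT in period B with log baseline as covariate) as the dependent variable of the primary comparison. Use it in every case, without a normality pre-test, and drop the conditional square-root rule for IELT.
3. Back-transform to the fold change per arm and the between-arm ratio of geometric means, each with a 95% confidence interval.

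The cost is about two sentences and no new data. The geometric mean already in the plan needs positive times, so the log scale asks nothing further of the records.

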18. SCHEDULE AND PROPOSED END DATE

The selection and inclusion period for patients to participate in the study is set between June 2019 and August 2019.

The planned date for the commencement of the trial and the treatment is the end of June and July 2019. The planned date for the completion of the exercise program in both groups is predicted to be at the end of August 2019.

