19. INTERVIEWS, QUESTIONNAIRES OR INSTRUMENTS TO BE USED IN THE TRIAL

The IELT measurements will be collected by self-registration after each week of treatment (APPENDIX I).

In order to collect the information regarding the perception of ejaculation, the Premature Ejaculation Profile (PEP) will be used (Patrick et al., 2009), a self-reported instrument consisting of four measurements (perceived control over ejaculation, personal stress related to ejaculation, satisfaction with sexual relationships, and interpersonal difficulty related to ejaculation). These will give an overall profile and score (Patrick et al., 2009), where the lowest scores express the lowest performance. The reliability coefficient between ranges from 0.66 to 0.83 and its validity was contrasted with dapoxetine and Intravaginal Ejaculation Latency Times (IELT). This instrument was validated in American and European trials, with people from Germany, France, England, Italy and Poland involved (Giuliano et al., 2008) although it has been used also in the Spanish community (Bar-Or, Salottolo, Orlando, Winkler, & Group, 2012; Buvat, Tesfaye, Rothman, Rivas, & Giuliano, 2009).

The Premature Ejaculation Diagnostic Tool (PEDT) will be used for the diagnosis. It takes five measurements in order to evaluate difficulty in delaying the ejaculation, ejaculation occurring before the patient wanted it, ejaculation with little stimulation, frustration related to premature ejaculation, and the couple's opinion about ejaculation. The test-retest reliability is 0.82 and all values statistically distinguish and differentiate statistically between PE and non-PE patients.

The Golombok-Rust Inventory of Sexual Satisfaction (GRISS) will also be applied. This is a brief 28-question questionnaire to assess the existence and severity of sexual problems in both members of a heterosexual relationship (Rust & Golombok, 1985, 1986). This questionnaire provides separate scores for men and women on 3 shared scales (avoidance, non-sensitivity, and dissatisfaction) and 6 gender-specific scales (impotence, premature ejaculation, anorgasmia, vaginismus, infrequency, and lack of communication) with acceptable values of reliability and validity (Rust & Golombok, 1985, 1986). The instrument was validated in the English community and is already being used in Spain in the official Master's degree in Sexology at the University of Almeria (García González, 2013; López Lorente, 2013).

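### The baseline (period A) of the primary IELT fold change is stated inconsistently in Sections 9, 14 and 19, and the planned dates do not hold the design that Section 9 describes

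*Protocol*

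**What the plan says.** Section 14 makes the IELT fold change the main evaluation parameter. The numerator is "calculated using the geometric averages of the post-treatment IELT (period B") and the denominator is "the IELT at the beginning of the treatment that served as a baseline (period A"). Neither period is given a length or a position relative to the first exercise.

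Section 9 says "the control will be intra-subject" and that the data to "establish the baseline of each group will be collected during a period of a similar length to the treatment period". Section 16 fixes that length: "The duration of the treatment will be 7 weeks".

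Section 19 gives the protocol's one explicit IELT schedule: "The IELT measurements will be collected by self-registration after each week of treatment". It mentions no recording before treatment begins or after it ends.

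On dates, Section 18 sets inclusion from June to August 2019 and the start of trial and treatment at the end of June and July 2019. It then states: "The planned date for the completion of the exercise program in both groups is predicted to be at the end of August 2019". Section 5.12 repeats the 2019 inclusion period but prints a trial start of July 2017 and an end of September 2017.

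**The concern.** A separate period of about seven weeks and a value at the beginning of treatment are different measurements. The only stated recording schedule matches neither clearly: a record made after each week of treatment first appears when one week of exercises has been done. Two teams following this protocol in good faith could therefore compute the primary ratio with different denominators. One of them might find that it had not recorded IELT in the period it needed.

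The baseline carries more weight than usual here. There is no untreated arm, so each therapy's own effect is judged against its baseline. If the denominator contains treated time and the therapy already has some effect by then, part of the benefit is counted as baseline. The contrast between arms would be affected only so far as early response differs between them.

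The calendar adds to the problem, because the dates leave no room for the baseline period that Section 9 describes. A later analysis plan could set window lengths. It could not recover pre-treatment IELT that had not been recorded.

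**Working it through.** **Treatment length.** Section 5.10 gives the four exercises 1, 3, 2 and 1 weeks: 1 + 3 + 2 + 1 = 7 weeks. This reproduces the figure in Section 16.

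**Period definitions side by side.**

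| Source | Period A | Period B |
|---|---|---|
| Section 9 | separate period, similar in length to treatment (about 7 weeks) | not defined |
| Section 14 | beginning of treatment, length not given | post-treatment, length not given |
| Section 19 | no pre-treatment recording named | no post-treatment recording named |

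**Direction of a possible bias.** Let F be the fold change against an untreated baseline. Let k be the ratio of IELT in the record used as period A to untreated IELT. The reported value is F / k. If period A is untreated, k = 1 and nothing is lost. If it is the first treatment-week record and therapy has already lengthened IELT, k > 1, and a true F above 1 moves toward 1. The protocol gives no information on k, so no size can be stated.

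**Calendar** (2019, first and last day both counted).

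- Available, 1 June to 31 August: 30 + 31 + 31 = 92 days, or 13.1 weeks.
- Needed for a 7-week baseline plus treatment: (7 + 7) × 7 = 98 days, before any period B. 98 − 92 = 6 days short. A man enrolled on 1 June finishes on 6 September. Finishing by 31 August would need enrolment by 26 May, before inclusion opens.
- Check against the start window: a 7-week baseline before a 30 June treatment start would have to begin on 12 May, also before inclusion opens.
- Treatment alone, with no baseline period: 7 × 7 = 49 days, and 31 August − 48 days = 14 July. Later starts overrun; a 31 July start ends on 17 September. Section 18 allows starts in July and inclusion through August.

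**Sensitivity of the calendar result.**

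- If similar length means 6 weeks: (6 + 7) × 7 = 91 days. A man enrolled on 1 June finishes on 30 August and one enrolled on 2 June on 31 August. Nobody enrolled later fits.
- If the September end in Section 5.12 is read as 30 September 2019 (an assumption): 30 September − 97 days = 25 June, so 7 + 7 weeks fits men enrolled by then. The 25 June enrolee has no days left for period B. The 1 June enrolee finishes on 6 September and has 30 − 6 = 24 days.

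**Section 5.12.** As printed, the trial ends in September 2017, before the inclusion period of June to August 2019 in the same section.

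**The case against.** The strongest reply is that the text can be read as coherent. Section 19 says when IELT is recorded during treatment; it does not say that it is recorded at no other time. Section 9 states that baseline data will be collected. Section 13 requires a mean self-reported IELT below 120 seconds for inclusion, and Section 12 sends selection records before entry, so some untreated IELT must exist. The register in Annex 1 has a blank week field and is not tied to treatment weeks. The Section 14 phrase can mean the value just before the first exercise. Appendix 3 describes week 1 as awareness of the pelvic floor, with stop-start practice from week 2, so the first weekly record may carry little effect. Any bias toward 1 would not create a false claim of benefit. The end-August date is a prediction and covers the exercise program only.

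Most of this stands, and it limits what can be said. A reader might infer that there is no untreated baseline at all; the documents do not support that, since Section 19 is silent on the point rather than exclusive. A reader might infer that nobody can complete the design on time. That needs a full 7-week baseline and end August as a hard stop. A reader might put a figure on the dilution; any such figure would be pure assumption. Nor does anything say that late entrants would be given a shorter baseline at the single clinic.

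What the reply does not remove is the inconsistency. Even on the most favourable reading of Section 14, Section 9 still asks for a period of about seven weeks, and Section 19 still schedules no recording for period A or period B. A screening IELT used for eligibility is not stated to be period A.

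**Conclusion.** The point holds as an inconsistency in the primary endpoint's definition, together with a schedule that does not hold the design. Period A is a separate period of about 7 weeks in Section 9 and the beginning of treatment in Section 14. Section 19 names no recording before or after treatment for either period.

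Bias toward 1 in the within-group fold change is possible, not certain. It requires that the first treatment-week record serves as baseline and that therapy already has an effect by then. Its size cannot be derived from the protocol.

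The calendar shortfall is 98 days needed against 92 available, taking similar length as 7 weeks and end August as the limit. With 6 weeks, only men enrolled on 1 or 2 June fit. With a 30 September 2019 end, only those enrolled by about 25 June fit, with little or no time for period B. Two findings need no assumption about the baseline: treatment starts after 14 July overrun end August, and the 2017 dates in Section 5.12 precede its own inclusion period. The 2017 entries are probably a misprinted year, but they need correcting. This should be settled before recruitment, because a baseline that was not recorded cannot be recovered.

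**What to change.** Use one definition in Sections 9, 14 and 19:

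- **Period A:** intercourse IELT on the existing weekly register, before the first exercise, with its length stated.
- **Period B:** a fixed window after week 7, counted from the treatment start date and identical in both arms. Counting from the start date keeps the window from moving with individual progress, since Appendix 3 lets men repeat activities until the objectives are reached.
- **Section 19:** state that the register is completed in period A, during treatment and in period B.
- **Sections 5.12 and 18:** reconcile the dates so that the end date equals last inclusion + A + 7 weeks + B, or close inclusion earlier.

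The wording changes cost little, and the Annex 1 register already has a row for intercourse. The real cost is time. With a 7-week period A, the end date falls at least 7 + 7 = 14 weeks after last inclusion, plus period B. If inclusion stays open to 31 August 2019, A and treatment alone run to 6 December 2019. Closing inclusion earlier shortens this but leaves less time to recruit.
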